## **Accelerometer**

Each subject will wear an accelerometer at baseline and prior to final assessments (MTI Actigraph by Actigraph) to measure habitual level of physical activity, which affects insulin sensitivity. Accelerometers are effective tools for the objective measurement of physical activity [183] because they have the ability to continuously record physical activity data and such data can be used to estimate METs of activity. They provide more detailed information than pedometers, which only measure walking steps, and help get around the recall bias of questionnaires. We are currently using the MTI Actigraph in adolescents in our other diabetes studies; therefore, we are familiar with their use in this population and have the necessary computer software and interpretation skills. Data collected from the accelerometers will be analyzed prior to the insulin clamp to verify that the subjects are sedentary.

## **Urine Metalmatrix Proteins**

At each clamp visit, 5 mls of urine will be frozen from each subject at -20C and used to assay protein levels and activity of the MMPs 2, 9, and 13.

## **Measurements made during bicycle ergometer testing**

During all bicycle tests,  $VO_2$  (ml/kg/min) and  $VCO_2$  (ml/kg/min) will be measured, breath-by-breath, at rest and during exercise. Arm blood pressure (by auscultation) and heart rate (by 12-lead ECG) will be obtained every minute during exercise. Cardiac status will be monitored throughout each test by 12-lead ECG. The respiratory exchange ratio (RER) will be calculated as  $VCO_2$  (ml/kg/min)/ $VO_2$  (ml/kg/min). A snack will be provided to subjects following completion of the  $VO_2$ max test.

## **Cardiac Echocardiographic Measurements**

Standard two dimensional and Doppler echocardiography will be performed by an echocardiographer under the supervision of cardiologist [name] at the University of Colorado Health Sciences Center Heart Center, using [184] to ascertain the presence of left ventricular systolic dysfunction, regional wall motion abnormalities (suggestive of coronary artery disease), pericardial disease or significant valvular pathology. Chamber sizes, LV end-systolic and diastolic chamber dimensions and wall thickness, fractional shortening and the area-length method for measurement of cardiac volume in order to measure ejection fraction will be quantitated by standard techniques for all individuals.

Diastolic function will be assessed by standard echocardiographic parameters (E and A wave velocities, E:A ratio, E wave deceleration time, pulmonary vein Doppler) as well as tissue Doppler of both the septal and lateral mitral annuli (E' and A' velocities, E':A' ratio, E:E' ratio), flow propagation determined by color M-mode, and longitudinal and circumferential strain with speckle tracking. [name], MD and the echocardiographer, who have expertise in echocardiography and these techniques, will be blinded to the diagnostic status of the participant and will supervise and/or perform acquisition of all of the echocardiographic data as well as perform all of the measurements and interpretation. Echocardiograms will be obtained with a commercially available ultrasound system (VingMed Vivid FiVe, GE, Milwaukee, WI) and stored on magneto-optical discs for offline measurement and interpretation using EchoPac (GE, Milwaukee, WI). Subjects will be examined in the left lateral decubitus position using standard parasternal, short-axis, and apical views. All recordings and measurements will be obtained by the same observer according to the recommendations of the American Society of Echocardiography and will always be performed at the same time of day for each subject to avoid the possible influence of circadian rhythm on left ventricular diastolic function (Voutilinen). All cardiac valves will be examined to rule out significant valvular disease. Left ventricular mass (LVM) will be calculated using the following formula:  $LVM (g) = 0.8 \times 1.04 [(LVEDD + IVST + PWT)^3 - (LVEDD)^3] + 0.6$ , where LVEDD is left ventricle end diastolic internal diameter, IVST is interventricular septal thickness, and PWT is left ventricular posterior wall thickness. Cardiac imaging will be performed fasting in the AM at rest following the 3 day study diet, and also during and immediately following exercise on the bicycle ergometer.

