### **3. Eligibility**

#### **a) Inclusion Criteria**

1. Adolescents 12-21 years of age with type 1 diabetes (defined as having positive GAD, ICA and/or IA2A antibodies as well as insulin requirement)
2. Willing to consent for participation in study
3. Both normal weight (BMI 5-85%) and overweight/obese T1D subjects (BMI > 85%) will be enrolled to allow sub-analysis of the effects of BMI on IR, CVD and response to metformin in T1D.

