### **Visit 3 (Exercise Visit)**

UCD Exercise Lab (12th floor inpatient University Hospital): Subjects will be asked not to have caffeine or exercise strenuously for 3 days prior to this visit. They will be asked to continue to check their blood sugars at least 4 times a day (as we normally recommend) during this time. Study personnel will call the subject to discuss the numbers, and adjust insulin if needed. Subjects will be studied in the AM fasting. Subject will be questioned regarding compliance, adverse events, changes in concomitant medications and medical history, height, weight, BP, and blood sugars.

Patients will undergo brachial artery ultrasound with 5 minute blood pressure cuff occlusion and endoPAT to measure endothelial function. They will also undergo carotid artery ultrasound and Dynapulse in order to measure arterial stiffness. They will then have a resting ECG and echocardiogram performed by an echocardiographer. Following resting measurements, subjects will complete a VO2max exercise test on a stationary bicycle. During and immediately following the completion of an exercise test, they will undergo another brief echocardiogram.

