## **Brachial Artery Diameter**

Endothelial function will be assessed at the Heart Center of the University of Colorado Health Sciences Center. The brachial artery method will be utilized following the protocol described by Celermajer et al [185, 186], that measures dilation of the brachial artery by ultrasound. The brachial artery diameter will be measured using B-mode ultrasound images, with the use of a GE VingMed ultrasound system and a 10.0-mHz linear-array transducer. Scans will be obtained with the subject at rest and following reactive hyperemia. The subjects will lie quietly for 10 minutes before the first scan. The brachial artery will be scanned in longitudinal section 2-15 cm above the elbow. Depth and gain settings will be set to optimize images of the interface between the lumen and arterial wall. When a satisfactory transducer position is found, the skin will be marked and the arm stationed in the same position throughout the study. Increased flow will then be induced by inflation of a pneumatic tourniquet

placed around the forearm (proximal to the scanned part of the artery) to a pressure of 200 mmHg for 5 minutes, followed by release. Hyperemic response will be measured one minute after cuff deflation. Thereafter, 10 minutes will be allowed for recovery of the vessel, after which an additional resting scan will be performed. The diameter of the vessel will be measured in every case by two independent observers blinded to the status of the participant, stage of the experiment and stage of the study. Flow-mediated dilatation will be calculated by each observer and recorded. The average of the two observations will be used in analysis. The arterial diameter will be measured at a fixed distance from the anatomical marker (such as a fascial plane or a vein seen in cross section) with the use of ultrasonic calipers. Measurements will be taken from the anterior to the posterior “m” line at end-diastole, coincidentally with the R wave on a continuously recorded electrocardiogram. For the reactive hyperemia scan, measurements of diameter will be taken 60 seconds after deflation of the cuff. A minimum of three cardiac cycles will be analyzed for each scan, and the measurements for each observer recorded. The vessel diameter in scans obtained after reactive hyperemia will be expressed as a percentage of the average diameter of the artery in the two resting (or control) scans (considered as 100 percent).

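### The stated echo blinding, to diagnostic status, masks nothing in an all-T1D trial, and the plan does not mask circumferential strain readings to visit

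*Combined protocol and SAP*

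**What the plan says.** All references are to the combined protocol and SAP.

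- **Echo blinding (Cardiac Echocardiographic Measurements).** The cardiologist and echocardiographer "will be blinded to the diagnostic status of the participant". The section names no other masking.
- **Who acquires and reads (same section).** They supervise or perform "acquisition of all of the echocardiographic data as well as perform all of the measurements and interpretation". In addition, "All recordings and measurements will be obtained by the same observer". Images are "stored on magneto-optical discs for offline measurement and interpretation using EchoPac". Nothing is said about coding files, removing visit labels or reading order.
- **Population (Inclusion Criteria).** "Adolescents 12-21 years of age with type 1 diabetes". No control or type 2 group is enrolled.
- **Comparator (Brachial Artery Diameter).** Vessel diameter for flow-mediated dilation (FMD) is measured by "two independent observers blinded to the status of the participant, stage of the experiment and stage of the study".
- **Treatment masking (Study Visits, Intervention; Visit 4).** The pharmacist randomizes, the placebo looks identical, and investigators and subjects are blinded.
- **Echo visits (Visit 3; Visit 7 repeats it).** "Subject will be questioned regarding compliance, adverse events, changes in concomitant medications and medical history". The section does not say who asks.
- **Rank of the outcomes.** Primary Outcome Measures lists circumferential strain, and FMD is under Secondary Outcome Measures. Section 6.2.2 lists mean change in strain as a secondary endpoint, and the Analysis plan names glucose infusion rate as the primary analysis.

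**The concern.** A blinding statement should hide whatever could influence the reading. In a study with non-diabetic controls, that is diagnosis. In this before-and-after randomized trial, it is treatment arm, visit, the participant's earlier value and clinical information. The echo section protects against the first kind of knowledge, which is irrelevant here, and does not mention the second.

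The person who acquires a Visit 7 scan knows that it is a follow-up, and the section allows that person to measure it too. A reader who remembers the baseline strain may pull the follow-up value towards it, or towards an expected improvement. The plan asks for visit masking of FMD, so it was evidently thought relevant and feasible for ultrasound. Strain, which the outcome list ranks above FMD, has no equivalent statement.

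**Working it through.** The plan gives no figure to reproduce here. The check compares the masking provisions and then asks what each gap could do to the planned analyses.

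**1. Provisions side by side**

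| Masked to | Strain | FMD |
|---|---|---|
| Diagnosis or participant status | Stated, but diagnosis is constant | Stated |
| Treatment arm | Through trial-level double-blinding | Through trial-level double-blinding |
| Stage of the study (visit) | Not stated | Stated |
| Independent second observer | No, one observer | Yes, two |

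**2. A constant visit shift.** Suppose every follow-up reading moves by a constant *c*.
- Between arms: (mean change on metformin + *c*) − (mean change on placebo + *c*) = the original difference. The shift cancels.
- Change on change: Cov(X, ΔY + *c*) = Cov(X, ΔY) and Var(ΔY + *c*) = Var(ΔY). The correlations and regression slopes planned under Secondary Analysis are unchanged.
- Within-arm mean change does move by *c*, but the plan specifies no within-arm test of strain.

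**3. Anchoring on the baseline value.** Suppose the recorded follow-up is (1 − λ)Y₁ + λY₀, where Y₀ and Y₁ are the baseline and follow-up values that unaffected reading would give. The recorded change is then (1 − λ)(Y₁ − Y₀). The treatment difference and any change-on-change slope shrink by the factor (1 − λ). If λ differs between participants, it also adds noise. The documents give no basis for a value of λ.

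**4. Clues to arm.** For a bias that does not cancel, the reader would have to learn of side effects, infer the arm and shift the reading. In SD units:

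bias = (difference between arms in the share guessed) × (reading shift)

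Type I error follows from the noncentral *t* with 2*n* − 2 degrees of freedom and noncentrality bias × √(*n*/2), at the plan's two-sided α of 0.0125. The sizes are *n* = 40 per arm (80 recruited, √20) and *n* = 30 per arm (60 completers, √15). The guessing and shift inputs are **assumptions**, and none comes from the documents.

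| Assumed difference in share guessed | Assumed shift (SD) | Bias (SD) | Share of the 0.645 SD target | Type I error, 40 per arm | Type I error, 30 per arm |
|---|---|---|---|---|---|
| 20 points | 0.10 | 0.02 | 3% | 0.0128 | 0.0128 |
| 20 points | 0.25 | 0.05 | 8% | 0.0146 | 0.0141 |
| 20 points | 0.50 | 0.10 | 16% | 0.0214 | 0.0190 |
| 30 points | 0.50 | 0.15 | 23% | 0.0337 | 0.0278 |

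The results run from essentially nominal to well over twice nominal, depending entirely on the assumptions. The table shows the mechanism and is not an estimate for this trial.

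**The case against.** The strongest reply has four parts.

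- **Arm is already masked.** This stands. A reader might infer from the echo section that strain is read without any useful masking. The Intervention and Visit 4 text rules that out, although it does not say whether the echocardiographer counts as an investigator.
- **Silence is not unmasking.** This also stands. The plan never says that visit is known at reading, and offline measurement would allow masked reading. The gap is a missing safeguard. It does not show that readings are unmasked.
- **Visit knowledge does little harm to the treatment comparison.** This largely stands. It is tempting to say that visit-linked drift distorts the change-on-change analyses, but step 2 shows that a constant shift does not. Nor can the reader know the change in insulin resistance when the Visit 7 scan is acquired, because the second clamp comes at Visit 8. Only reading error that varies between participants, or that scales with the change, is left.
- **Unmasking through gastrointestinal effects is speculative.** This mostly stands. The preliminary metformin data report good tolerability under blinding, and the drop-out section reports neither dose reduction nor notable excess attrition against placebo in the group's obesity study. The questioner at the echo visits may not be the echocardiographer. The route is possible but not strongly supported.

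The contrast between a primary and a secondary outcome should also not be pressed, since section 6.2.2 itself places strain among the secondary endpoints. Using a single observer has a benefit too, because it limits inter-observer variability.

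None of this rescues the sentence itself: blinding to diagnosis has no function in this trial, and the visit masking written for FMD is absent for strain.

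**Conclusion.** Minor, but real. The stated echo blinding rule is inoperative because diagnosis does not vary. The double-blind design covers treatment arm, and nothing covers visit, the earlier reading or clinical information. The exposure is non-constant reading error: mainly anchoring on a remembered baseline value, which would shrink estimated effects, and less likely arm-related clues. Its size cannot be derived from the documents. The documents do not support the stronger inference that the strain comparison is biased in favour of metformin or that its type I error is inflated by a known amount. That would need guessing rates and reading shifts that no passage supplies.

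**What to change.** In Cardiac Echocardiographic Measurements, replace the reference to diagnostic status with masking to treatment arm, visit and clinical information. Then add the procedure:

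1. Code the EchoPac files, already stored for offline measurement, so that participant identity and visit are hidden.
2. Have the same reader measure each participant's Visit 3 and Visit 7 studies in random order, after Visit 7.
3. Keep any on-the-day safety look separate from this research reading.

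The rule should be in place before reading starts, because a value already seen cannot be unseen.

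The cost is protocol wording, the coding work and research readings that wait until after Visit 7. No extra reader, procedure or participant visit is needed, and the single-reader design is kept. A reader who also acquired the scans may still recall a participant, so masking is improved but not complete.

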## **Brachial Artery Diameter**

Endothelial function will be assessed at the Heart Center of the University of Colorado Health Sciences Center. The brachial artery method will be utilized following the protocol described by Celermajer et al [185, 186], that measures dilation of the brachial artery by ultrasound. The brachial artery diameter will be measured using B-mode ultrasound images, with the use of a GE VingMed ultrasound system and a 10.0-mHz linear-array transducer. Scans will be obtained with the subject at rest and following reactive hyperemia. The subjects will lie quietly for 10 minutes before the first scan. The brachial artery will be scanned in longitudinal section 2-15 cm above the elbow. Depth and gain settings will be set to optimize images of the interface between the lumen and arterial wall. When a satisfactory transducer position is found, the skin will be marked and the arm stationed in the same position throughout the study. Increased flow will then be induced by inflation of a pneumatic tourniquet

placed around the forearm (proximal to the scanned part of the artery) to a pressure of 200 mmHg for 5 minutes, followed by release. Hyperemic response will be measured one minute after cuff deflation. Thereafter, 10 minutes will be allowed for recovery of the vessel, after which an additional resting scan will be performed. The diameter of the vessel will be measured in every case by two independent observers blinded to the status of the participant, stage of the experiment and stage of the study. Flow-mediated dilatation will be calculated by each observer and recorded. The average of the two observations will be used in analysis. The arterial diameter will be measured at a fixed distance from the anatomical marker (such as a fascial plane or a vein seen in cross section) with the use of ultrasonic calipers. Measurements will be taken from the anterior to the posterior “m” line at end-diastole, coincidentally with the R wave on a continuously recorded electrocardiogram. For the reactive hyperemia scan, measurements of diameter will be taken 60 seconds after deflation of the cuff. A minimum of three cardiac cycles will be analyzed for each scan, and the measurements for each observer recorded. The vessel diameter in scans obtained after reactive hyperemia will be expressed as a percentage of the average diameter of the artery in the two resting (or control) scans (considered as 100 percent).

### **Dynapulse Measurements**

The Dynapulse Pathway system (PulseMetric, Inc., San Diego, CA) is a noninvasive portable system to measure brachial artery distensibility, utilizing a standard sphygmomanometer cuff inflated in the same fashion as a sphygmomanometer to obtain blood pressure. The instrument derives brachial artery distensibility using the technique of pulse waveform analysis of arterial pressure signals obtained from the sphygmomanometer.

### **Endo-PAT Measurements**

RH-PAT testing is a non-invasive technique that combines the traditional flow-mediated dilatation with pneumatic fingertip probes to measure arterial pulse wave amplitude and provide an objective measure of endothelial function. Briefly, the patient sits in a reclining chair with the hands at heart level and propped in a comfortable position such that the fingers are hanging freely. Fingertip probes are placed on both index fingers and pulse wave amplitudes are recorded for the duration of the study. After 5 min of baseline measurement, arterial flow to the nondominant arm is occluded for 5 min using a BP cuff inflated to 40 mmHg above systolic pressure. After the 5-min occlusion, the cuff is rapidly deflated to allow for reactive or flow-mediated hyperemia. Pulse wave amplitudes are recorded for at least 5 min after the cuff is deflated. An integrated software program compares the ratio of arterial pressure in the two fingers before and after the occlusion to calculate the RH-PAT score. The RH-PAT score is calculated as the ratio of the average pulse wave amplitude measured over 60 s starting 1 min after cuff deflation to the average pulse wave amplitude measured at baseline. This ratio is normalized to the concurrent signal from the contralateral finger to correct for changes in systemic vascular tone.

### **Carotid Intima-Media Thickness (CIMT)**

The ultrasound transducer is placed on one side of the subject's neck, a single image is obtained and frozen, and software is used to automatically detect the intima media thickness. CIMT will be used to assess differences in atherosclerotic burden between lean, obese and diabetic subjects, and to assist in interpreting differences in FMD between the groups.

### **Exercise Prescription**

The final visit will conclude with education regarding the importance of physical activity, diet and lifestyle modification to mediate the risks associated with sedentary lifestyle and an exercise prescription designed to increase physical activity. The exercise information and prescription are the standard of care used in our Children’s Hospital Colorado Pediatric Metabolic Syndrome Clinic, designed by the Children’s Hospital Colorado Pediatric Exercise Physiologist. This Exercise Physiologist will also be available to the study for consultation as needed. Families will be provided with standard information about follow up care with their primary care provider and contact information for Children’s Hospital Colorado Diabetes and Child Health Clinics if needed regarding any abnormal study findings. In addition, the subject/family will be provided with copies of their study lab results, DEXA scan, physical activity monitoring and exercise test. Study staff will also call the family after the conclusion of the study to check-in on the recommended follow up care and answer any questions about test results.

## **V. Description, Risks and Justification of Procedures and Data Collection**

### **A. Study Duration**

#### **1. Planned Duration of the Entire Study**

The anticipated duration for the study is 5 years.

#### **2. Duration of Participation for Each Subject**

Subject participation consists of 9 visits for study:

**Visit 1 (Screen Visit):** This visit will last approximately 3.5 hours, during which time patients will have demographics and medical history and allergies confirmed, blood drawn and a urine sample taken for laboratory measures, and anthropometrics completed, , and be given an accelerometer to wear for the following 7 days, be instructed on medication administration and glucose monitoring, and subsequent visits will be scheduled.

**Visits 2 and 6 (MRI Visit):** Patients will come to the Brain Imaging Center or CHC Radiology for an MRI. Total duration of visit will be approximately 1 hour.

**Visits 3 and 7 (Exercise Visit):** Patients will come to the adult CTRC in the 12th floor adult CTRC inpatient area building for a brachial artery ultrasound, carotid ultrasound and Dynapulse measurements, resting echocardiogram, VO2max tests and post-exercise echocardiogram as described. Total duration of visit will be approximately 2.5 hours.

**Visits 4 and 8 (Clamp Visit):** Patients will be admitted to the Pediatric CTRC overnight for stabilization of blood glucose as described. The following morning, clamp studies will be completed. Total duration of visit will be approximately 19 hours.

**Visit 5:** Interim visit will allow assessment of compliance, GI side effects, adverse events, changes in concomitant medications and medical history, height, weight, BP, WC, HC, HbA1c, safety labs and blood sugars, and medication dispensed. This visit will last approximately 1 hour.

**Phone Calls:** A minimum of 2 phone calls will be made to discuss blood sugars and any issues with medications. These calls will last approximately 10 minutes. Other calls may be made if subjects experience illness or other problems with blood sugars or medications.

